#### **8.3.2 Discontinuation from Study Treatment**

A subject should be discontinued from treatment for any of the following reasons:

- Withdrawal of consent or subject requests study treatment discontinuation for any reason
- Occurrence of any medical condition or circumstance that exposes the subject to substantial risk and/or does not allow the subject to adhere to the requirements of the protocol
- Confirmed disease progression ([Section 10.2.1.1](#))

- Any unacceptable toxicity, SAE, clinically significant AEs, severe laboratory abnormality, intercurrent illness, or other medical condition which indicates to the Investigator that continued participation is not in the best interest of the subject
- Subject experiences any Grade 4 adverse event, with the exception of those listed in [Table 9-2](#)
- Pregnancy
- Subject failure to comply with protocol requirements or study-related procedures. [Dosing compliance issues should be reviewed on a case-by-case basis with Medical Monitor.]
- Termination of the study by the Sponsor or regulatory authority

Subjects who experience unacceptable toxicity directly attributable to pembrolizumab may continue on study and receive ADU-S100 as single agent study treatment with approval by the Medical Monitor.

If a subject's study treatment (ADU-S100 and/or pembrolizumab) is discontinued, this will not result in automatic withdrawal of the subject from the study. The Investigator will provide a reason for treatment discontinuation. Subjects who discontinue treatment will be encouraged to complete EOT and follow-up assessments.

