**Table 9-2 Toxicities Requiring Dose Modification or Treatment Discontinuation**

Any Grade 4 AEs will lead to permanent treatment discontinuation with the exception of:
 
 
• Neutropenia lasting <math>\leq 5</math> days that is not associated with fever or other clinical symptoms
 
• Lymphopenia or leukopenia
 
• Electrolyte abnormalities not associated with clinical sequelae or deemed not clinically significant and are corrected with appropriate management or supplementation within 72 hours of onset
 

Drug Induced Liver Injury (DILI) will lead to permanent study treatment discontinuation as indicated by serum chemistry values consistent with Hy's Law criteria (all 3 of the following must co-exist):
 
 
• ALT or AST <math>\geq 3\times</math> institutional upper limit of normal (ULN)
 
• Total bilirubin <math>\geq 2\times</math> ULN
 
• Alkaline phosphatase <math>< 2\times</math> ULN
 

Grade 4 injection site reaction will lead to discontinuation of ADU-S100
Grade 3 or higher infusion-related reaction will lead to discontinuation of pembrolizumab

Any Grade 3 AEs may lead to dose modification or delay of either ADU-S100 or pembrolizumab after consultation with the medical monitor with the exception of:
 
 
• Serum lipase and/or serum amylase (asymptomatic) CTCAE Grade 3 <math>< 7</math> consecutive days
 
• Nausea and vomiting that resolves within 2 days after starting optimal anti-emetic therapy
 
• Thrombocytopenia without significant bleeding
 
• Anemia that resolves within 7 days in the absence of transfusion
 
• Diarrhea that resolves within 2 days after starting optimal anti-diarrhea treatment
 
• Hypertension that resolves within 7 days after starting treatment
 
• Infection or fever in the absence of neutropenia that resolves within <math>< 5</math> days
 
• Rash or photosensitivity that resolves within 7 days after starting treatment
 
• Fatigue that resolves within 7 days
 

Grade 2 or 3 clinically significant injection site reactions will lead to delay and/or dose modification of ADU-S100 (See Section 9.5.4 )

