	Grade 3-4	Permanently discontinue	
 
• Increase frequency of monitoring to every 1-2 days
 
• 1.0-2.0 mg/kg/day methylprednisolone or IV equivalent
 
• Add prophylactic antibiotics for opportunistic infections
 
• Consult gastroenterologist
 
	
 
• If returns to grade 2, taper steroids over 1 month
 
• If does not improve in >3-5 days, worsens or rebounds, add mycophenolate mofetil 1g BID. If no response within an additional 3-5 days, consider other immunosuppressants per local guidelines
 

Endocrinopathies	Asymptomatic TSH elevation	Continue IO therapy	If TSH <0.5 X LLN or TSH >2 X ULN, or consistently out of range in 2 subsequent measurements: include fT4 at subsequent cycles as indicated; consider endocrinology consult	
	Symptomatic endocrinopathy	Withhold a	Evaluate endocrine function Consider pituitary scan 
 
• If symptomatic with abnormal lab/pituitary scan, 1-2 mg mg/kg/day methylprednisolone or PO equivalent and initiate appropriate hormone therapy
 
• If no abnormal lab/pituitary MRI scan but symptoms persist, repeat labs in 1-3 weeks/ MRI in 1 month
 
	If improves (with or without hormone replacement), taper steroids over 1 month and consider prophylactic antibiotics for opportunistic infections. IO therapy should resume. Subjects with adrenal insufficiency may need to continue steroids with mineralocorticoid component.
	Suspicion of adrenal crisis (e.g. severe dehydration, hypotension, shock out of proportion to current illness)	Withhold until clinically stable or discontinue	
 
• Rule out sepsis
 
• Stress dose of IV steroids with mineralocorticoid activity
 
• IV fluids
 
• Consult endocrinologist
 
• If adrenal crisis ruled out, then treat as for symptomatic endocrinopathy
 
	
Creatinine Elevation	Grade 1	Continue IO therapy	Monitor creatinine weekly	
 
• If returns to baseline, resume routine creatinine monitoring per protocol
 
• If worsen, treat as Grade 2 or 3/4
 

irAE	SEVERITY per CTCAE v 5.0	DOSE MODIFICATION OR TREATMENT DELAY	MANAGEMENT	FOLLOW UP

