	Grade 3 based on the severity and type of reaction or Grade 4	Permanently discontinue		
Recurrent immune-mediated reactions	Recurrent Grade 2 pneumonitis Recurrent Grades 3 or 4	Permanently discontinue		
Inability to taper corticosteroid	Requirement for $\geq 10$ mg/day prednisone or equivalent for more than 12 weeks after last dose of pembrolizumab	Permanently discontinue		
Persistent immune-mediated reaction (excluding endocrinopathy)	Grades 2 or 3 adverse reactions lasting 12 weeks or longer after last dose of pembrolizumab	Permanently discontinue		
Infusion-related reactions	See Section 9.5.3			

\* Toxicity was graded per National Cancer Institute Common Terminology Criteria for Adverse Events. Version 5.0 (NCI-CTCAE v5.0).

a Resume treatment when adverse reaction improves to Grade 0 or 1 after corticosteroid taper

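### Appendix A's ungraded symptomatic-endocrinopathy row says to resume immunotherapy on improvement, which for a first Grade 4 event contradicts the permanent stop in Section 8.3.2 and Table 9-2

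*Protocol*

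**What the plan says.** Two parts of the protocol deal with stopping treatment for a severe immune-related event.

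**The stop rule.** Section 8.3.2 lists among the reasons to discontinue: "Subject experiences any Grade 4 adverse event, with the exception of those listed in" Table 9-2. The table states: "Any Grade 4 AEs will lead to permanent treatment discontinuation with the exception of" three cases. These are short neutropenia without fever or symptoms, lymphopenia or leukopenia, and electrolyte abnormalities that are corrected promptly and have no clinical consequence. Section 9.5.1 introduces the table in mandatory terms.

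**The irAE guidance.** Section 9.5.2 refers dose modification for immune-related adverse events (irAEs) to Appendix A. There, the symptomatic-endocrinopathy row says to withhold and, if the subject improves with or without hormone replacement, to "taper steroids over 1 month and consider prophylactic antibiotics for opportunistic infections. IO therapy should resume". The footnote attached to the withhold instruction reads: "Resume treatment when adverse reaction improves to Grade 0 or 1 after corticosteroid taper". The next row, for suspected adrenal crisis, says "Withhold until clinically stable or discontinue", and adds: "If adrenal crisis ruled out, then treat as for symptomatic endocrinopathy". Neither row nor the footnote sets a limit on the peak grade.

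**The concern.** A site treating a subject whose first Grade 4 endocrinopathy has come under control on hormone replacement finds two stated instructions. Appendix A says immunotherapy should restart. Table 9-2 says treatment ends permanently.

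Following the first means re-exposure after a life-threatening event that the protocol's own mandatory rule treats as a reason to stop. Following the second means loss, within the study, of first-line standard-of-care pembrolizumab for a subject who is clinically stable. Two sites could handle identical subjects differently, and each could point to protocol text in support.

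The gap is specific to this category. In Appendix A, pneumonitis, colitis, liver tests, creatinine and skin each have a row that permanently stops treatment at Grade 4, and so does the residual category for other reactions. Endocrinopathies is the only organ category without one.

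**Working it through.** There is no figure to reproduce, so the check sets the texts side by side for each way an endocrine event can arise.

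| Endocrine event | Section 8.3.2 and Table 9-2 | Appendix A | Result |
|---|---|---|---|
| First symptomatic event, peak Grade 3 or lower | No mandatory stop | Withhold, resume on improvement | Compatible |
| First symptomatic event, peak Grade 4, crisis not suspected | Permanent stop | Withhold, resume on improvement | Contradiction |
| Grade 4, crisis suspected | Permanent stop | Withhold until stable, or discontinue | Partial conflict |
| Grade 4, crisis suspected and then ruled out | Permanent stop | Handled under the symptomatic row | Contradiction |
| Recurrent Grade 4 | Permanent stop | Permanent stop | Agree |

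Step 1: is there an endocrine exception to the Grade 4 stop? The exceptions number three, and none is endocrine. Table 9-2 has separate lines for injection-site and infusion reactions, so drug-specific handling was written where it was wanted. There is no such line for endocrinopathy.

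Step 2: does another Appendix A row close the gap? The recurrent-reactions row stops treatment for "Recurrent Grade 2 pneumonitis Recurrent Grades 3 or 4" events, so it does not reach a first event. The steroid row stops a subject who still needs at least 10 "mg/day prednisone or equivalent for more than 12 weeks after last dose of pembrolizumab". That removes some subjects, but not one whose steroids are tapered successfully. The residual row with a Grade 4 stop is for reactions outside the named categories.

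Step 3: does any sentence rank the texts?

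- Section 9.5.1 says events in Table 9-2 require modification and/or discontinuation, and Table 9-2 says Grade 4 events will lead to a permanent stop. Both favour the stop.
- Appendix A describes itself as guidance, which also favours the stop, although that sentence ranks it only against institutional practice.
- Section 9.3.4 has Appendix A followed where appropriate. The same phrase covers the Section 9.5 interruption guidance, so it adds little alone.
- Section 9.5.2 sends irAE dose modification to Appendix A with no condition that Table 9-2 prevails. This points the other way.
- The last row of Table 9-2 brings in Appendix A's discontinuation criteria and is silent on its resume instructions.

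The weight of wording favours the stop, but no sentence says so.

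Step 4: do other provisions settle it? Section 9.5.1 requires Medical Monitor consultation before treatment resumes after a Table 9-2 event, but gives the Medical Monitor no rule to apply. Sections 8.3.2 and 9.5 allow ADU-S100 alone after toxicity directly attributable to pembrolizumab, which does not answer whether pembrolizumab may restart. Section 9.5.1 also ends treatment after an interruption of more than 6 weeks unless there is clinical benefit, which limits resumption without excluding it. Section 9.5.2 points to current prescribing information for updates, which is not available here.

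**The case against.** The strongest reply is that the ordinary reading is already clear. Table 9-2 is mandatory with a closed list of exceptions, Section 8.3.2 adopts that list, and Appendix A is guidance. On that reading the table sets a ceiling, the ungraded row operates beneath it, and a conflict appears only if silence about Grade 4 is taken as permission. Much of this stands. A reader might infer that the two rules are evenly balanced and the question wholly open; the documents do not support that, because the firmer wording is on the side of stopping. What remains is an unqualified instruction to resume, in the place to which Section 9.5.2 sends the site.

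Two further inferences should be resisted. First, Appendix A excludes endocrinopathy from its persistent-reaction stop, and a reader might take this as a sign that the missing Grade 4 stop is deliberate. That row covers only Grade 2 or 3 reactions lasting 12 weeks or longer, so it says nothing about Grade 4. Second, the redirect from the adrenal-crisis row might suggest that the symptomatic row routinely receives Grade 4 cases. Once crisis is ruled out, shock or dehydration may have another cause, such as the sepsis the row tells the site to rule out. The redirect shows that severe presentations can enter an ungraded row, not that the remaining endocrinopathy is Grade 4.

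It is also fair to say that the case is unobserved, that enrolment is nearly complete, and that Medical Monitor review makes an unreviewed restart unlikely. These points lower the priority. They do not make the two instructions consistent.

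**Conclusion.** The contradiction is real and narrow. It concerns a first Grade 4 symptomatic endocrinopathy, with a partial conflict in the adrenal-crisis row because holding until stability also falls short of a permanent stop. There is no conflict at Grade 3 or lower, and recurrent Grade 4 events stop under both texts. The protocol's wording favours the stop without stating that it prevails.

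The size is small. The protocol limits enrolment to about 20 evaluable subjects, and Section 5.2.2 reports 16 treated as of 17 December 2020. The one endocrine event among the treatment-related serious events listed there is a Grade 3 hypophysitis, where the texts agree. No Grade 4 endocrine event is reported.

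A reader might infer that the efficacy analysis is at risk. The documents do not support this: no endpoint definition depends on which rule is followed, and the SAP summarises the objective response rate over all treated subjects. This is a low-priority correction to safety wording. It rests on the protocol text alone and assumes that the current pembrolizumab label, which could not be checked, does not already settle the point.

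**What to change.** Make two changes.

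1. In the symptomatic-endocrinopathy row of Appendix A, limit the resume instruction to events whose peak severity was Grade 3 or lower.
2. In Section 9.5.2, add one sentence stating that Section 8.3.2 and Table 9-2 govern all Grade 4 immune-related adverse events, including those that enter through the adrenal-crisis row.

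This applies the protocol's own mandatory rule and leaves the existing allowance for ADU-S100 alone as it is.

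Only if the sponsor's clinical team intends treatment to resume once a subject is stable on hormone replacement should the opposite course be taken: list that case among the Grade 4 exceptions in Table 9-2, to which Section 8.3.2 already refers.

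Either course needs one clinical decision by the sponsor and a short amendment, which requires IRB/EC approval under Section 14.3. It adds no visits, procedures or subjects.

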## Appendix B: RECIST V1.1 CRITERIA

Adapted from ([Eisenhauer et al. 2009](#)).

**Imaging Methods:** The same method of assessment and same technique should be used at baseline and all follow up assessments. CT is the preferred method of tumor evaluation for this study. If lesion being followed cannot be imaged but can be assessed by clinical examination, measurements taken by usage of calipers will be acceptable. MRI is the preferred method for brain and bone lesions. If CT is performed instead of MRI, ambiguous results may be confirmed by MRI. MRI is also indicated if CT scan is contraindicated (e.g. allergy to contrast dye). Chest x-rays, positron emission tomography (PET), ultrasound and bone scans will not be used for response assessments in this study.

- 1) Target lesions:** Measurable lesions, up to a maximum of 5 total lesions (up to 2 lesions per organ) representing all involved organs should be identified as target lesions at baseline. They should be selected based on size and accuracy for repeated measurements.

At each assessment, the sum of diameters (SoD; longest diameter for non-nodal lesions, and short axis for nodal lesions) will be calculated and recorded in source documents. If 2 lesions coalesce, the measurement of the coalesced mass is used. If a target lesion splits, the sum of the parts is used. If a target lesion is considered to have disappeared, 0 mm should be recorded. If a target lesion becomes too small to measure, a default value of 5 mm should be recorded.

The baseline SoD should be used as a comparison for any objective tumor regression. The lowest SoD (nadir) should be used as reference for evaluating progression.

### **Response Criteria for target lesions**

Response Criteria	Evaluation of Target Lesions
Complete Response (CR):	Disappearance of all non-nodal target lesions. In addition, any pathological lymph nodes assigned as target lesions must have a reduction in short axis to < 10 mm 
Partial Response (PR):	At least a 30% decrease in the sum of diameter of all target lesions, taking as reference the baseline sum of diameters.
Progressive Disease (PD):	At least a 20% increase in the sum of diameter of all measured target lesions, taking as reference the smallest sum of diameter of all target lesions recorded at or after baseline. In addition to the relative increase of 20%, the sum must also demonstrate an absolute increase of at least 5 mm  .
Stable Disease (SD):	Neither sufficient shrinkage to qualify for PR or CR nor an increase in lesions which would qualify for PD
Unknown (UNK)	Progression has not been documented and one or more target lesions have not been assessed or have been assessed using a different method than baseline.

 SOD for CR may not be zero when nodal lesions are part of target lesions

 Following an initial CR, a PD cannot be assigned if all non-nodal target lesions are still not present and all nodal lesions are <10 mm in size. In this case, the target lesion response is CR

- 2) Non-target lesions:** All non-measurable lesions are non-target lesions. Measurement of these lesions are not required; instead, the presence, absence or unequivocal progression of each are to be recorded. Following CR, non-target and new lymph node lesions are to be measured to determine if they have become pathological in size.
- 3) New lesions:** these are to be recorded separately in the eCRF. Finding of new lesions should not be attributed to differences in scanning technique, change in imaging modality or findings thought to represent something other than tumor. A lesion identified in an anatomic location that was not scanned at baseline is considered a new lesion.

If a new lesion is equivocal, continue assessment until etiology can be clarified. If at the next assessment the new lesion is confirmed, the date of progression should be recorded as the date the new lesion was first noted.

**Evaluation of Overall Response:**

Target Lesion	Non-target lesion	New Lesion	Objective Status
CR	CR	No	CR
CR	Non-CR/ Non-PD	No	PR
CR	Indeterminate or missing	No	PR
PR	Non-CR/ Non-PD, Indeterminate or missing	No	PR
SD	Non-CR/ Non-PD, Indeterminate or missing	No	SD
Indeterminate or missing	Non-PD	No	Indeterminate
PD	Any	Yes or no	PD
Any	PD	Yes or no	PD
Any	Any	Yes	PD

CR=complete response; PR=partial response; SD=stable disease; PD= progression; non-CR/non-PD=criteria for neither CR nor PD have been met.

All noted regressions should be confirmed at next tumor assessment.

## Appendix C: IRECIST CRITERIA

Increasing experience indicates that traditional response criteria may not be sufficient to fully characterize activity in this new era of immunotherapeutic agents. For example, agents such as anti-CTLA-4 and anti-PD1 and anti-PD-L1 exert anti-tumor activity by augmenting activation and proliferation of T-cells, thus leading to tumor infiltration by T cells and tumor regression rather than direct cytotoxic effects. In early trials of immune-based therapeutics in melanoma, investigators described unique response patterns, termed pseudo-progression, whereby subjects met the criteria based on traditional response criteria such as RECIST were noted to have late but deep and durable responses.

On the basis of these observations, a number of immune related criteria were developed and substantial variability in their usage across clinical studies were noted. This led to the development of iRECIST (immune RECIST) criteria by the RECIST working group in 2017 ([Seymour et al. 2017](#)).

iRECIST is based on RECIST criteria. There are no changes compared to RECIST to the recommendations regarding the method of measurement. All responses per iRECIST have a prefix of “i” (i.e. immune)—e.g. “immune” complete response (iCR) or partial response (iPR), and unconfirmed progressive disease (iUPD) or confirmed progressive disease (iCPD) to differentiate them from responses assigned using RECIST 1.1. Similar nomenclature is used for stable disease (iSD).

The major concept is resetting the bar once progression is identified per RECIST v1.1. This initial progression is identified as iUPD per iRECIST. Note that treatment past RECIST 1.1 PD should only be considered if:

- 1) Subject clinically stable
- 2) There is no worsening of ECOG status
- 3) No clinically relevant increase in disease related symptoms
- 4) No requirement for intensified management of disease related symptoms (analgesics, radiation, palliative care)

Any new lesions identified at iUPD will be assessed and subcategorized into those that qualify as target lesions (new lesion, target; maximum of 5 target lesions and maximum of 2 per organ should be identified) or non-target lesions (new lesion, non-target) and will be recorded separately from the original target and non-target lesions.

Progression must be confirmed on the next scan that is completed 4 to 9 weeks following initial iUPD; if confirmed, this will be categorized as iCPD (for immune confirmed progression). As such, should an iCR, iPR or iSD follow the initial iUPD, the next progression that follows will also be categorized as iUPD. However, if the next assessment following iUPD is not done or not evaluable, then if the following assessment is progression, then it should be labeled as iCPD.

Progression is only confirmed (i.e. iCPD) if the next scan following iUPD indicates a  $\geq 5$ mm increase in target lesions, any size increase in non-target lesions, a  $\geq 5$ mm increase in new lesion target lesions, any size increase in new lesions non-target lesions, or the appearance of another

new lesion. If progression is not confirmed, and there is no subsequent iSD, iPR or iCR, the reasons for a lack of confirmation must be recorded. The reasons should include:

1. Not stable
2. Worsening of ECOG status
3. Clinical increase in disease related symptoms
4. Treatments stopped and subject not reassessed/ imaging not performed
5. Subject has died
6. iCPD never occurred

In this case, for statistical purposes, the progression event date should be the iUPD date.

### Assignment of Timepoint Response Using iRECIST

	Timepoint response with no previous iUPD in any category	Timepoint response with previous iUPD in any category*
Target lesions: iCR; non-target lesions: iCR; new lesions: no	iCR	iCR
Target lesions: iCR; non-target lesions: non-iCR/non-iUPD; new lesions: no	iPR	iPR
Target lesions: iPR; non-target lesions: non-iCR/non-iUPD; new lesions: no	iPR	iPR
Target lesions: iSD; non-target lesions: non-iCR/non-iUPD; new lesions: no	iSD	iSD
Target lesions: iUPD with no change, or with a decrease from last timepoint; non-target lesions: iUPD with no change, or decrease from last timepoint; new lesions: yes	Not applicable	New lesions confirm iCPD if new lesions were previously identified and they have increased in size ( $\geq 5$ mm in sum of measures for new lesion target or any increase for new lesion non-target) or number; if no change is seen in new lesions (size or number) from last timepoint, assignment remains iUPD
Target lesions: iSD, iPR, iCR; non-target lesions: iUPD; new lesions: no	iUPD	Remains iUPD unless iCPD is confirmed on the basis of a further increase in the size of non-target disease (does not need to meet RECIST 1.1 criteria for unequivocal progression)
Target lesions: iUPD; non-target lesions: non-iCR/non-iUPD, or iCR; new lesions: no	iUPD	Remains iUPD unless iCPD is confirmed on the basis of a further increase in sum of measures $\geq 5$ mm; otherwise, assignment remains iUPD
Target lesions: iUPD; non-target lesions: iUPD; new lesions: no	iUPD	Remains iUPD unless iCPD is confirmed based on a further increase in previously identified target lesion iUPD in sum of measures $\geq 5$ mm or non-target lesion iUPD (previous assessment need not have shown unequivocal progression)
Target lesions: iUPD; non-target lesions: iUPD; new lesions: yes	iUPD	Remains iUPD unless iCPD is confirmed on the basis of a further increase in previously identified target lesion iUPD sum of measures $\geq 5$ mm, previously identified non-target lesion

	Timepoint response with no previous iUPD in any category	Timepoint response with previous iUPD in any category*
		iUPD (does not need to be unequivocal), or an increase in the size or number of new lesions previously identified
Target lesions: non-iUPD or progression; non-target lesions: non-iUPD or progression; new lesions: yes	iUPD	Remains iUPD unless iCPD is confirmed on the basis of an increase in the size or number of new lesions previously identified

\*Previously identified in assessment immediately before this timepoint. “i” indicates immune responses assigned using iRECIST. iCR=complete response; iPR=partial response; iSD=stable disease; iUPD=unconfirmed progression; non-iCR/non-iUPD=criteria for neither CR nor PD have been met; iCPD=confirmed progression; RECIST=Response Evaluation Criteria in Solid Tumors.

